11.3 CIDOFOVIR (VISTIDE®, GILEAD SCIENCES)

Cidofovir is an FDA-approved antiviral drug for the treatment of CMV retinitis among patients with AIDS. Cell-based *in vitro* studies and animal model studies have demonstrated this agent's antiviral activity against certain orthopoxviruses. Currently, its efficacy in the treatment of vaccinia-related complications in humans is unknown. According to the CDC, VIG is recommended as first line of therapy. Cidofovir may be considered as a secondary treatment, and will only be used when VIG therapy is not effective [Medical Management of Smallpox (Vaccinia) Vaccine Adverse Reactions: Vaccinia Immune Globulin and Cidofovir. Last updated September 28, 2009. Available at: <http://www.bt.cdc.gov/agent/smallpox/vaccination/mgmt-adv-reactions.asp>].

11.4 ENZALUTAMIDE

Please see FDA-approved packet insert for Enzalutamide for complete agent information.

11.4.1 Description and formulation

Enzalutamide (XTANDI ©) is an androgen receptor inhibitor. The chemical name is 4-{3-[4-cyano-3-(trifluoromethyl)phenyl]-5,5-dimethyl-4-oxo-2-sulfanylideneimidazolidin-1-yl}-2-fluoro-*N*-methylbenzamide. Enzalutamide is a white crystalline non-hygroscopic solid. It is practically insoluble in water. XTANDI is provided as liquid-filled soft gelatin capsules for oral administration. Each capsule contains 40 mg of enzalutamide as a solution in caprylocaproyl polyoxylglycerides. The inactive ingredients are caprylocaproyl polyoxylglycerides, butylated hydroxyanisole, butylated hydroxytoluene, gelatin, sorbitol sorbitan solution, glycerin, purified water, titanium dioxide, and black iron oxide.

11.4.2 Source

Medivation and Astellas Inc. have reviewed the proposed clinical trial design and have agreed to provide enzalutamide for the trial.

11.4.3 Storage

Store enzalutamide capsules at 20°C to 25°C (68°F to 77°F) in a dry place and keep the container tightly closed. Excursions permitted from 15°C to 30°C (59°F to 86°F).

11.4.4 Stability

The company providing the IND drug will also provide the expiration date for each lot allocated to this study.

11.4.5 Dosage and Administration

Enzalutamide 160 mg (four 40 mg capsules) administered orally once daily. Swallow capsules whole. Enzalutamide can be taken with or without food.

11.4.6 Adverse Effects

Seizure

In the randomized clinical trial, 7 of 800 (0.9%) patients treated with enzalutamide 160 mg once daily experienced a seizure. No seizures occurred in patients treated with placebo. Seizures occurred from 31 to 603 days after initiation of enzalutamide. Patients experiencing seizure were permanently discontinued from therapy and all seizures resolved. There is no clinical trial experience re-administering enzalutamide to patients who experienced seizures. The safety of enzalutamide in patients with predisposing factors for seizure is not known because these patients were excluded from the trial. These exclusion criteria included a history of seizure, underlying brain injury with loss of consciousness, transient ischemic attack within the past 12 months, cerebral vascular accident, brain metastases, brain arteriovenous malformation or the use of concomitant medications that may lower the seizure threshold. Because of the risk of seizure associated with enzalutamide use, patients should be advised of the risk of engaging in any activity where sudden loss of consciousness could cause serious harm to themselves or others.

Other adverse events

The most common adverse drug reactions ($\geq 5\%$) reported in patients receiving enzalutamide in the randomized clinical trial were asthenia/fatigue, back pain, diarrhea, arthralgia, hot flush, peripheral edema, musculoskeletal pain, headache, upper respiratory infection, muscular weakness, dizziness, insomnia, lower respiratory infection, spinal cord compression and cauda equina syndrome, hematuria, paresthesia, anxiety, and hypertension. Grade 3 and higher adverse reactions were reported among 47% of enzalutamide-treated patients and 53% of placebo-treated patients. Discontinuations due to adverse events were reported for 16% of enzalutamide-treated patients and 18% of placebo-treated patients. The most common adverse reaction leading to treatment discontinuation was seizure, which occurred in 0.9% of the enzalutamide-treated patients compared to none (0%) of the placebo-treated patients.

Laboratory Abnormalities

In the randomized clinical trial, Grade 1-4 neutropenia occurred in 15% of patients on enzalutamide (1% Grade 3-4) and in 6% of patients on placebo (no Grade 3-4). The incidence of Grade 1-4 thrombocytopenia was similar in both arms; 0.5% of patients on enzalutamide and 1% on placebo experienced Grade 3-4 thrombocytopenia. Grade 1-4 elevations in ALT occurred in 10% of patients on enzalutamide (0.3% Grade 3-4) and 18% of patients on placebo (0.5% Grade 3-4). Grade 1-4 elevations in bilirubin occurred in 3% of patients on enzalutamide and 2% of patients on placebo.

Infections

In the randomized clinical trial, 1.0% of patients treated with enzalutamide compared to 0.3% of patients on placebo died from infections or sepsis. Infection-related serious adverse events were reported in approximately 6% of the patients on both treatment arms.

Falls and Fall-related Injuries

In the randomized clinical trial, falls or injuries related to falls occurred in 4.6% of patients treated with enzalutamide compared to 1.3% of patients on placebo. Falls were not associated with loss of consciousness or seizure. Fall-related injuries were more severe in patients treated with enzalutamide and included non-pathologic fractures, joint injuries, and hematomas.

Hallucinations

In the randomized clinical trial, 1.6% of patients treated with enzalutamide were reported to have Grade 1 or 2 hallucinations compared to 0.3% of patients on placebo. Of the patients with hallucinations, the majority were on opioid-containing medications at the time of the event. Hallucinations were visual, tactile, or undefined.

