2.1.2 Exclusion Criteria

- A. Immunocompromised status due to:
 - Human immunodeficiency virus (HIV) positivity.

- Active autoimmune diseases such as Addison's disease, Hashimoto's thyroiditis, systemic lupus erythematosus, Sjogren syndrome, scleroderma, myasthenia gravis, Goodpasture syndrome or active Grave's disease. Patients with a history of autoimmunity that has not required systemic immunosuppressive therapy or does not threaten vital organ function including CNS, heart, lungs, kidneys, skin, and GI tract will be allowed.
 - Other immunodeficiency diseases
- B. Chronic administration (defined as daily or every other day for continued use > 14 days) of corticosteroids deemed systemic by investigator within 28 days before the first planned dose of PSA-TRICOM. Use of inhaled steroids, nasal sprays, and topical creams for small body areas is allowed.
- C. Serious intercurrent medical illness that, in the judgment of the investigator, would interfere with patient's ability to carry out the treatment program.
- D. History of seizure, including any febrile seizure, loss of consciousness, or transient ischemic attack, or any condition that may pre-dispose to seizure (e.g., prior stroke, brain arteriovenous malformation, head trauma with loss of consciousness requiring hospitalization).
- E. Other medications used for urinary symptoms including 5-alpha reductase inhibitors (finasteride and dutasteride) and alternative medications known to alter PSA (eg phytoestrogens and saw palmetto)
- F. History of prior chemotherapy
- G. History of prior immunotherapy within the last 3 years
- H. Major surgery within 4 weeks prior to enrollment (Day 1 visit).
- I. History of allergic reactions attributed to compounds of similar chemical or biologic composition to *enzalutamide* or poxviral vaccines (e.g., vaccinia vaccine)
- J. Known allergy to eggs, egg products, aminoglycoside antibiotics (for example, gentamicin or tobramycin).
- K. History of atopic dermatitis or active skin condition (acute, chronic, exfoliative) that disrupts the epidermis
- L. Previous serious adverse reactions to smallpox vaccination
- M. Unable to avoid close contact or household contact with the following high-risk individuals for three weeks after the Day 1 vaccination: (a) children \leq 3 years of age, (b) pregnant or nursing women, (c) individuals with prior or concurrent extensive eczema or other eczemoid skin disorders, or (d) immunocompromised individuals, such as those with HIV.

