- N. Receipt of an investigational agent within 30 days (or 60 days for an antibody-based therapy) before the first planned dose of study drugs.
- O. Patients who test positive for HBV or HCV
- P. Use of herbal products that may decrease PSA levels (e.g. saw palmetto)
- Q. Any gastrointestinal disease that could hinder the absorption of enzalutamide
- R. Uncontrolled hypertension (SBP>170/ DBP>105)

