3.5 CONCURRENT THERAPIES

Concurrent hormonal therapy not otherwise stipulated in the protocol will not be allowed. Concurrent anticancer treatment with chemotherapy, systemic glucocorticoids (topical and inhaled steroids allowed), radiation therapy, major surgical procedures for prostate cancer, and nonprotocol-related immunotherapy will not be permitted.

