5.1 EXCLUDED MEDICATIONS

While patients on protocol treatment, all medications required for the health of the patient are allowed with the following exceptions:

- Concurrent chemotherapy
- Concurrent radiation therapy
- Concurrent immunotherapy
- Concurrent anti-cancer radionuclides
- Concurrent systemic corticosteroid use (daily or every other day for continued use > **14 days**; See section **2.1.2**)
- Concomitant use of secondary hormonal treatments

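### Exclusion 2.1.2 D does not name drugs that lower the seizure threshold, a group kept out of the trial behind the protocol's enzalutamide seizure data

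*Combined protocol and SAP*

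**What the plan says.** Section 11.4.6 (Adverse Effects, Seizure) gives the seizure experience of the randomized trial at 160 mg daily: 7 of 800 patients on enzalutamide, none on placebo, with onset between day 31 and day 603. It then limits that evidence: "The safety of enzalutamide in patients with predisposing factors for seizure is not known because these patients were excluded from the trial". The exclusions it goes on to list end with "brain arteriovenous malformation or the use of concomitant medications that may lower the seizure threshold".

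This trial's own seizure screen is exclusion 2.1.2 D. It begins "History of seizure, including any febrile seizure, loss of consciousness, or transient ischemic attack" and continues with "any condition that may pre-dispose to seizure (e.g., prior stroke, brain arteriovenous malformation, head trauma with loss of consciousness requiring hospitalization". No medication is mentioned.

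On concomitant drugs, section 5.1 states that "all medications required for the health of the patient are allowed with the following exceptions", followed by six classes: chemotherapy, radiation, immunotherapy, anticancer radionuclides, systemic corticosteroids and secondary hormonal treatments. Section 3.5 opens with "Concurrent hormonal therapy not otherwise stipulated in the protocol will not be allowed" and otherwise deals with anticancer treatment, systemic steroids, prostate cancer surgery and immunotherapy. Section 11.4.7 covers interactions through CYP enzymes.

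**The concern.** The protocol identifies a group in whom the drug's safety is unknown and screens out most of that group at entry. It says nothing explicit about one part of it, men already on a drug that lowers the seizure threshold. All patients receive the dose at which the 7 seizures occurred (section 3.2), and the earliest onset reported, day 31, falls inside a 3-month course. These men have non-metastatic disease and ECOG status 0 or 1, and surveillance is one of their standard options (section 1.2.7). An avoidable exposure of unknown risk is therefore harder to justify than it would be in advanced disease.

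The safeguards in place act mainly after enrolment. They are the advice on hazardous activities in 11.4.6, and in 3.6.1 the removal for medical circumstances and the stop after any seizure. A check at entry would act before exposure.

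**Working it through.** **The plan's own figure.** From 11.4.6, 7/800 = 0.00875 = 0.875%, which rounds to the stated 0.9%. The exact (Clopper-Pearson) 95% interval is 0.35% to 1.79%.

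**Item-by-item comparison.**

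| Source-trial exclusion listed in 11.4.6 | Counterpart in this protocol |
|---|---|
| Seizure history | 2.1.2 D, including febrile seizure |
| Brain injury with loss of consciousness | 2.1.2 D (head trauma; loss of consciousness) |
| TIA in the previous 12 months | 2.1.2 D, with no time limit |
| Cerebral vascular accident | 2.1.2 D (prior stroke) |
| Brain arteriovenous malformation | 2.1.2 D |
| Brain metastases | Not in D; inclusion G requires negative staging for metastatic disease |
| Drugs that may lower the seizure threshold | None named |

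**Could another provision supply the missing item?**

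- *The open clause in D.* It refers to a condition, and its three examples are stroke, a vascular malformation and head trauma. Section 11.4.6 lists drug use as an item of its own beside such conditions. Where 2.1.2 means to exclude products it names them: B names corticosteroids, E includes "alternative medications known to alter PSA (eg phytoestrogens and saw palmetto", and P reads "Use of herbal products that may decrease PSA levels (e.g. saw palmetto".
- *2.1.2 C.* It concerns serious intercurrent illness, not drugs.
- *Sections 3.5 and 5.1.* Neither names the class, and the default in 5.1 is permission.
- *Section 11.4.7.* A drug is restricted there only on CYP grounds.
- *Section 11.4.* It refers to the package insert for full agent information. That text is not in the documents, and a label reference is not an eligibility criterion.
- *Section 3.1, retreatment.* Course 2 depends on time on study and PSA recovery, and 3.4.4 adds scans. No medication check is specified.

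**Size.** The documents give neither the share of users nor their relative risk. Purely as an assumption, take 5% to 30% of the maximum 38 patients as users, with 2 to 5 times the reference risk. Excess expected seizures = 38 × share × 0.00875 × (relative risk − 1):

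- low end: 38 × 0.05 × 0.00875 × 1 = 0.017
- high end: 38 × 0.30 × 0.00875 × 4 = 0.40

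The span is more than twentyfold and depends wholly on the assumed inputs. The base rate also reflects follow-up in which seizures occurred as late as day 603, against 3 months per course here. The range shows only that any effect in this trial would probably be a fraction of one event; it is not an estimate.

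**The case against.** The best reply is that D already closes the gap. Its examples are introduced as examples, so the clause is open, and 11.4.6 places these drugs among the exclusions tied to predisposing factors. An investigator reading the two together could decline a user. That stands as a matter of discretion: D leaves room to decline, but does not require it, and two investigators could decide differently.

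A second reply is that D is this protocol's own screen and is in places stricter than the source list: TIA at any time, any febrile seizure, any loss of consciousness. This also stands. A reader might infer from the table that one of six applicable exclusions was dropped. The documents do not support that measure, because 11.4.6 presents its items as included among the criteria, so the full list is unknown. Nor do they show whether the omission was an oversight or a choice.

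Third, the 0.9% figure does not directly describe anyone here. The 800 matches the enzalutamide arm of the trial in docetaxel-treated metastatic disease in section 1.2.1, and that section says no data exist in this population. This is fair. The point therefore rests on the protocol's statement that safety with predisposing factors is unknown, not on the rate. Unknown safety does not compel exclusion, but it is the ground on which closely matching risk factors are already excluded.

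Finally, it may seem inconsistent to exclude a user at entry yet tolerate the same drug started during a course. The situations differ. At entry the exposure can be avoided, whereas during a course the patient may need the new drug. A reader might also infer that the source trial banned such drugs during treatment; 11.4.6 describes exclusion criteria and does not say so.

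**Conclusion.** The gap is real but modest. The protocol does not name use of threshold-lowering drugs as a bar to entry or retreatment, and no other section restricts the class. On the plain text a current user can be enrolled or given course 2 unless the investigator declines by judgment. This assumes that the word condition in D has its ordinary medical sense.

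A reader might go further and conclude that the trial carries a raised seizure risk. The documents give no prevalence or excess risk for users, so that does not follow. They also contain no list defining the drug class.

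The value of a change depends partly on timing. This version is dated 12/5/17, and section 1.2.12.1 already reports immune data from 12 patients on enzalutamide alone. If enrolment is complete, the entry criterion has little reach, but the check before course 2 would still serve men not yet retreated. The sample size, primary comparison and analysis are unaffected.

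**What to change.** Add to 2.1.2 D, as a separate item, current use of any drug on a sponsor-defined list of medicines that can lower the seizure threshold. The list is needed because the class is otherwise open-ended; it should say whether a washout makes a patient eligible. Repeat the check before course 2, alongside the restaging scans in 3.4.4. For new prescriptions during a course, add a line to 11.4.7 in its existing style: avoid if possible, and if the drug is needed the investigator reviews whether to hold or stop enzalutamide. This is preferable to a ban in 5.1, which could deny a patient necessary treatment.

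The cost is one phrase, a short list, one advisory line and one extra check. Exclusions B, E and P already require a medication review at screening. There may be a few more screen failures; the documents give no basis for a number, and it depends on how broad the list is. A hold would shorten that patient's 3-month course and should be recorded.

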11.4.7 Drug Interactions

Drugs that Inhibit or Induce CYP2C8

Co-administration of a strong CYP2C8 inhibitor (gemfibrozil) increased the composite area under the plasma concentration-time curve (AUC) of enzalutamide plus N-desmethyl enzalutamide in healthy volunteers. Co-administration of enzalutamide with strong CYP2C8 inhibitors should be avoided if possible. If co-administration of enzalutamide with a strong CYP2C8 inhibitor cannot be avoided, reduce the dose of enzalutamide.

The effects of CYP2C8 inducers on the pharmacokinetics of enzalutamide have not been evaluated *in vivo*.

Co-administration of enzalutamide with strong or moderate CYP2C8 inducers (e.g., rifampin) may alter the plasma exposure of enzalutamide and should be avoided if possible. Selection of a concomitant medication with no or minimal CYP2C8 induction potential is recommended.

Drugs that Inhibit or Induce CYP3A4

Co-administration of a strong CYP3A4 inhibitor (itraconazole) increased the composite AUC of enzalutamide plus N-desmethyl enzalutamide by 1.3 fold in healthy volunteers

The effects of CYP3A4 inducers on the pharmacokinetics of enzalutamide have not been evaluated *in vivo*.

Co-administration of enzalutamide with strong CYP3A4 inducers (e.g., carbamazepine, phenobarbital, phenytoin, rifabutin, rifampin, rifapentine) may decrease the plasma exposure of enzalutamide and should be avoided if possible. Selection of a concomitant medication with no or minimal CYP3A4 induction potential is recommended. Moderate CYP3A4 inducers (e.g., bosentan, efavirenz, etravirine, modafinil, nafcillin) and St. John's Wort may also reduce the plasma exposure of enzalutamide and should be avoided if possible.

Effect of Enzalutamide on Drug Metabolizing Enzymes

Enzalutamide is a strong CYP3A4 inducer and a moderate CYP2C9 and CYP2C19 inducer in humans. At steady state, enzalutamide reduced the plasma exposure to midazolam (CYP3A4 substrate), warfarin (CYP2C9 substrate), and omeprazole (CYP2C19 substrate). Concomitant use of enzalutamide with narrow therapeutic index drugs that are metabolized by CYP3A4 (e.g., alfentanil, cyclosporine, dihydroergotamine, ergotamine, fentanyl, pimozone, quinidine, sirolimus

and tacrolimus), CYP2C9 (e.g., phenytoin, warfarin) and CYP2C19 (e.g., proton pump inhibitors (lansoprazole, omeprazole, pantoprazole, rabeprazole) and clopidogrel.) should be avoided, as enzalutamide may decrease their exposure. If co-administration with warfarin cannot be avoided, conduct additional INR monitoring.

13 APPENDIX A: PERFORMANCE STATUS CRITERIA

ECOG Performance Status Scale		Karnofsky Performance Scale	
Grade	Descriptions	Percent	Descriptions
0	Normal activity. Fully active, able to carry on all pre-disease performance without restriction.	100	Normal, no complaints, no evidence of disease.
		90	Able to carry on normal activity; minor signs or symptoms of disease.
1	Symptoms, but ambulatory. Restricted in physically strenuous activity, but ambulatory and able to carry out light or sedentary work (e.g., light housework, office work).	80	Normal activity with effort; some signs or symptoms of disease.
		70	Cares for self, unable to carry on normal activity or to do active work.
2	In bed < 50% of the time. Ambulatory and capable of all self-care, but unable to carry out any work activities. Up and about > 50% of waking hours.	60	Requires occasional assistance, but is able to care for most of his/her needs.
		50	Requires considerable assistance and frequent medical care.
3	In bed > 50% of the time. Capable of only limited self-care, confined to bed or chair > 50% of waking hours.	40	Disabled, requires special care and assistance.
		30	Severely disabled, hospitalization indicated. Death not imminent.
4	100% bedridden. Completely disabled. Cannot carry on any self-care. Totally confined to bed or chair.	20	Very sick, hospitalization indicated. Death not imminent.
		10	Moribund, fatal processes progressing rapidly.
5	Dead.	0	Dead.

15 APPENDIX C : ON STUDY AND FOLLOW-UP EVALUATIONS

COHORT 1

	Arm A (Enzalutamide only)	Arm B (Enzalutamide + PSA-TRICOM)
Prior to Enrollment	Screening for eligibility, Informed consent, NIH Advanced Directives Form ¹	Screening for eligibility, Informed consent, NIH Advanced Directives form ¹
Within 8 weeks of initiating treatment	*Apheresis , Lab work (HIV, Hep B and C), baseline scans (MRI/CT and bone scans), EKG	*Apheresis , Lab work (HIV, Hep B and C), baseline scans (MRI/CT and bone scans), EKG
Within 16 days of beginning treatment (day -16 to day 1)	Baseline history and physical exam, ECOG status, Research Blood, CBC, Acute, Hepatic, Mineral Panels, LDH, CK, Uric Acid, Total Protein, TBNK, PSA, testosterone, PAP (prostatic acid phosphatase), dihydrotestosterone (DHT), sex hormone-binding globulin (SHBG), dehydroepiandrosterone (DHEA), luteinizing hormone (LH), follicle-stimulating hormone (FSH), androstenedione prolactin, estradiol Randomization	Baseline history and physical exam, ECOG status, Research Blood, CBC, Acute, Hepatic, Mineral Panels, LDH, CK, Uric Acid, Total Protein, TBNK, PSA, testosterone, PAP (prostatic acid phosphatase), dihydrotestosterone (DHT), sex hormone-binding globulin (SHBG), dehydroepiandrosterone (DHEA), luteinizing hormone (LH), follicle-stimulating hormone (FSH), androstenedione prolactin, estradiol Randomization
Day 1	Enzalutamide day 1 month 1 (daily dose of 160 mg)	Enzalutamide day 1 month 1 + PSA-TRICOM (Prostvac-V) dose 1
Week 3	Physical examination Research Blood, CBC, Acute, Hepatic, Mineral Panels, LDH, CK, Uric Acid, Total Protein,	Physical examination Research Blood, CBC, Acute, Hepatic, Mineral Panels, LDH, CK, Uric Acid, Total Protein,

	Arm A (Enzalutamide only)	Arm B (Enzalutamide + PSA-TRICOM)
	TBNK, PSA, testosterone, PAP, dihydrotestosterone (DHT), sex hormone-binding globulin (SHBG), dehydroepiandrosterone (DHEA), luteinizing hormone (LH), follicle-stimulating hormone (FSH), androstenedione prolactin, estradiol	TBNK, PSA, testosterone, PAP, dihydrotestosterone (DHT), sex hormone-binding globulin (SHBG), dehydroepiandrosterone (DHEA), luteinizing hormone (LH), follicle-stimulating hormone (FSH), androstenedione prolactin, estradiol PSA-TRICOM (Prostvac-F) dose 1
Week 5	Physical examination Research Blood, CBC, Acute, Hepatic, Mineral Panels, LDH, CK, Uric Acid, Total Protein, TBNK, PSA, testosterone, PAP, dihydrotestosterone (DHT), sex hormone-binding globulin (SHBG), dehydroepiandrosterone (DHEA), luteinizing hormone (LH), follicle-stimulating hormone (FSH), androstenedione prolactin, estradiol Enzalutamide day 1 month 2 (daily dose of 160 mg)	Physical examination Research Blood, CBC, Acute, Hepatic, Mineral Panels, LDH, CK, Uric Acid, Total Protein, TBNK, PSA, testosterone, PAP, dihydrotestosterone (DHT), sex hormone-binding globulin (SHBG), dehydroepiandrosterone (DHEA), luteinizing hormone (LH), follicle-stimulating hormone (FSH), androstenedione prolactin, estradiol Enzalutamide day 1 month 2 + PSA-TRICOM (Prostvac-F) dose 2
Week 9	Physical examination , CBC, Acute, Hepatic, Mineral Panels, LDH, CK, Uric Acid, Total Protein, TBNK, PSA, testosterone, PAP, dihydrotestosterone (DHT), sex hormone-binding globulin (SHBG), dehydroepiandrosterone (DHEA), luteinizing hormone (LH), follicle-stimulating hormone (FSH), androstenedione	Physical examination , CBC, Acute, Hepatic, Mineral Panels, LDH, CK, Uric Acid, Total Protein, TBNK, PSA, testosterone, PAP, dihydrotestosterone (DHT), sex hormone-binding globulin (SHBG), dehydroepiandrosterone (DHEA), luteinizing hormone (LH), follicle-stimulating hormone (FSH), androstenedione prolactin, estradiol

	Arm A (Enzalutamide only)	Arm B (Enzalutamide + PSA-TRICOM)
	prolactin, estradiol Enzalutamide day 1 month 3 (daily dose of 160 mg)	Enzalutamide day 1 month 3 + PSA-TRICOM (Prostvac-F) dose 3
Week 13	Physical examination , CBC, Acute, Hepatic, Mineral Panels, LDH, CK, Uric Acid, Total Protein, TBNK, PSA, testosterone, PAP, dihydrotestosterone (DHT), sex hormone-binding globulin (SHBG), dehydroepiandrosterone (DHEA), luteinizing hormone (LH), follicle-stimulating hormone (FSH), androstenedione prolactin, estradiol *Apheresis Enzalutamide therapy is discontinued	Physical examination , CBC, Acute, Hepatic, Mineral Panels, LDH, CK, Uric Acid, Total Protein, TBNK, PSA, testosterone, PAP, dihydrotestosterone (DHT), sex hormone-binding globulin (SHBG), dehydroepiandrosterone (DHEA), luteinizing hormone (LH), follicle-stimulating hormone (FSH), androstenedione prolactin, estradiol *Apheresis Enzalutamide therapy is discontinued PSA-TRICOM (Prostvac-F) dose 4
Week 15	, CBC, Acute, Hepatic, Mineral Panels, LDH, CK, Uric Acid, Total Protein, TBNK, PSA, testosterone, PAP, dihydrotestosterone (DHT), sex hormone-binding globulin (SHBG), dehydroepiandrosterone (DHEA), luteinizing hormone (LH), follicle-stimulating hormone (FSH), androstenedione prolactin, estradiol	, CBC, Acute, Hepatic, Mineral Panels, LDH, CK, Uric Acid, Total Protein, TBNK, PSA, testosterone, PAP, dihydrotestosterone (DHT), sex hormone-binding globulin (SHBG), dehydroepiandrosterone (DHEA), luteinizing hormone (LH), follicle-stimulating hormone (FSH), androstenedione prolactin, estradiol

	Arm A (Enzalutamide only)	Arm B (Enzalutamide + PSA-TRICOM)
Week 17	Physical examination Research Blood, CBC, Acute, Hepatic, Mineral Panels, LDH, CK, Uric Acid, Total Protein, TBNK, PSA, testosterone, PAP, dihydrotestosterone (DHT), sex hormone-binding globulin (SHBG), dehydroepiandrosterone (DHEA), luteinizing hormone (LH), follicle-stimulating hormone (FSH), androstenedione prolactin, estradiol	Physical examination Research Blood, CBC, Acute, Hepatic, Mineral Panels, LDH, CK, Uric Acid, Total Protein, TBNK, PSA, testosterone, PAP, dihydrotestosterone (DHT), sex hormone-binding globulin (SHBG), dehydroepiandrosterone (DHEA), luteinizing hormone (LH), follicle-stimulating hormone (FSH), androstenedione prolactin, estradiol PSA-TRICOM (Prostvac-F) dose 5
Week 21	Physical examination , CBC, Acute, Hepatic, Mineral Panels, LDH, CK, Uric Acid, Total Protein, TBNK, PSA, testosterone, PAP, dihydrotestosterone (DHT), sex hormone-binding globulin (SHBG), dehydroepiandrosterone (DHEA), luteinizing hormone (LH), follicle-stimulating hormone (FSH), androstenedione prolactin, estradiol	Physical examination , CBC, Acute, Hepatic, Mineral Panels, LDH, CK, Uric Acid, Total Protein, TBNK, PSA, testosterone, PAP dihydrotestosterone (DHT), sex hormone-binding globulin (SHBG), dehydroepiandrosterone (DHEA), luteinizing hormone (LH), follicle-stimulating hormone (FSH), androstenedione prolactin, estradiol PSA-TRICOM (Prostvac-F) dose 6
Week 25	Physical examination , CBC, Acute, Hepatic, Mineral Panels, LDH, CK, Uric Acid, Total Protein, TBNK, PSA, testosterone, PAP, dihydrotestosterone (DHT), sex hormone-binding globulin (SHBG), dehydroepiandrosterone	Physical examination , CBC, Acute, Hepatic, Mineral Panels, LDH, CK, Uric Acid, Total Protein, TBNK, PSA, testosterone, PAP, dihydrotestosterone (DHT), sex hormone-binding globulin (SHBG), dehydroepiandrosterone (DHEA), luteinizing hormone (LH),

	Arm A (Enzalutamide only)	Arm B (Enzalutamide + PSA-TRICOM)
	(DHEA), luteinizing hormone (LH), follicle-stimulating hormone (FSH), androstenedione prolactin, estradiol *Apheresis	follicle-stimulating hormone (FSH), androstenedione prolactin, estradiol *Apheresis PSA-TRICOM (Prostvac-F) is discontinued
Week 29	Physical examination , CBC, Acute, Hepatic, Mineral Panels, LDH, CK, Uric Acid, Total Protein, TBNK, PSA, testosterone, PAP, dihydrotestosterone (DHT), sex hormone-binding globulin (SHBG), dehydroepiandrosterone (DHEA), luteinizing hormone (LH), follicle-stimulating hormone (FSH), androstenedione prolactin, estradiol	Physical examination , CBC, Acute, Hepatic, Mineral Panels, LDH, CK, Uric Acid, Total Protein, TBNK, PSA, testosterone, PAP, dihydrotestosterone (DHT), sex hormone-binding globulin (SHBG), dehydroepiandrosterone (DHEA), luteinizing hormone (LH), follicle-stimulating hormone (FSH), androstenedione prolactin, estradiol
Up to Week 52 Every 4 weeks **	Physical examination , CBC, Acute, Hepatic, Mineral Panels, LDH, CK, Uric Acid, Total Protein, TBNK, PSA, testosterone, PAP, dihydrotestosterone (DHT), sex hormone-binding globulin (SHBG), dehydroepiandrosterone (DHEA), luteinizing hormone (LH), follicle-stimulating hormone (FSH), androstenedione prolactin, estradiol Research Blood (week 52 only)	Physical examination , CBC, Acute, Hepatic, Mineral Panels, LDH, CK, Uric Acid, Total Protein, TBNK, PSA, testosterone, PAP, dihydrotestosterone (DHT), sex hormone-binding globulin (SHBG), dehydroepiandrosterone (DHEA), luteinizing hormone (LH), follicle-stimulating hormone (FSH), androstenedione prolactin, estradiol Research Blood (week 52 only)

	Arm A (Enzalutamide only)	Arm B (Enzalutamide + PSA-TRICOM)
Beyond Week 52 Every 8 weeks (+/- 7 days)**	Physical examination , CBC, Acute, Hepatic, Mineral Panels, LDH, CK, Uric Acid, Total Protein, TBNK, PSA, testosterone, PAP, dihydrotestosterone (DHT), sex hormone-binding globulin (SHBG), dehydroepiandrosterone (DHEA), luteinizing hormone (LH), follicle-stimulating hormone (FSH), androstenedione prolactin, estradiol Research Blood (every 16 weeks)	Physical examination , CBC, Acute, Hepatic, Mineral Panels, LDH, CK, Uric Acid, Total Protein, TBNK, PSA, testosterone, PAP, dihydrotestosterone (DHT), sex hormone-binding globulin (SHBG), dehydroepiandrosterone (DHEA), luteinizing hormone (LH), follicle-stimulating hormone (FSH), androstenedione prolactin, estradiol Research Blood (every 16 weeks)
Once PSA reaches baseline value	Restaging Scans (MRI/CT and bone scans)	Restaging scans (MRI/CT and bone scans)
Course 2, Week 1	Enzalutamide day 1 month 1, course 2 (daily dose of 160 mg) Research labs including plasma VEGF levels	Enzalutamide day 1 month 1, course 2 Research labs including plasma VEGF levels
Course 2, Week 5	Physical examination Research Blood, CBC, Acute, Hepatic, Mineral Panels, LDH, CK, Uric Acid, Total Protein, TBNK, PSA, testosterone, PAP, dihydrotestosterone (DHT), sex hormone-binding globulin (SHBG), dehydroepiandrosterone (DHEA), luteinizing hormone (LH), follicle-stimulating	Physical examination Research Blood, CBC, Acute, Hepatic, Mineral Panels, LDH, CK, Uric Acid, Total Protein, TBNK, PSA, testosterone, PAP, dihydrotestosterone (DHT), sex hormone-binding globulin (SHBG), dehydroepiandrosterone (DHEA), luteinizing hormone (LH), follicle-stimulating hormone (FSH), androstenedione prolactin, estradiol

	Arm A (Enzalutamide only)	Arm B (Enzalutamide + PSA-TRICOM)
	
hormone (FSH)androstenedione prolactin, estradiol
 
Enzalutamide day 1 month 2 course 2 (daily dose of 160 mg)
	
Enzalutamide day 1 month 2 course 2

Course 2, Week 9	
Physical examination , CBC, Acute, Hepatic, Mineral Panels, LDH, CK, Uric Acid, Total Protein, TBNK, PSA, testosterone, PAP, dihydrotestosterone (DHT), sex hormone-binding globulin (SHBG), dehydroepiandrosterone (DHEA), luteinizing hormone (LH), follicle-stimulating hormone (FSH), androstenedione prolactin, estradiol
 
Enzalutamide day 1 month 3 course 2 (daily dose of 160 mg)
	
Physical examination , CBC, Acute, Hepatic, Mineral Panels, LDH, CK, Uric Acid, Total Protein, TBNK, PSA, testosterone, PAP, dihydrotestosterone (DHT), sex hormone-binding globulin (SHBG), dehydroepiandrosterone (DHEA), luteinizing hormone (LH), follicle-stimulating hormone (FSH), androstenedione prolactin, estradiol
 
Enzalutamide day 1 month 3 course 2

Course 2, Week 13	
Physical examination Research Blood, CBC, Acute, Hepatic, Mineral Panels, LDH, CK, Uric Acid, Total Protein, TBNK, PSA, testosterone, PAP, dihydrotestosterone (DHT), sex hormone-binding globulin (SHBG), dehydroepiandrosterone (DHEA), luteinizing hormone (LH), follicle-stimulating hormone (FSH), androstenedione prolactin, estradiol
	
Physical examination Research Blood, CBC, Acute, Hepatic, Mineral Panels, LDH, CK, Uric Acid, Total Protein, TBNK, PSA, testosterone, PAP, dihydrotestosterone (DHT), sex hormone-binding globulin (SHBG), dehydroepiandrosterone (DHEA), luteinizing hormone (LH), follicle-stimulating hormone (FSH), androstenedione prolactin, estradiol
 
Research labs including plasma VEGF levels

	Arm A (Enzalutamide only)	Arm B (Enzalutamide + PSA-TRICOM)
	
Research labs including plasma VEGF levels
 
*Apheresis Enzalutamide therapy is discontinued for course 2
	
*Apheresis Enzalutamide therapy is discontinued for course 2

Every 4 weeks thereafter	
Physical examination , CBC, Acute, Hepatic, Mineral Panels, LDH, CK, Uric Acid, Total Protein, TBNK, PSA, testosterone, PAP, dihydrotestosterone (DHT), sex hormone-binding globulin (SHBG), dehydroepiandrosterone (DHEA), luteinizing hormone (LH), follicle-stimulating hormone (FSH), androstenedione prolactin, estradiol
 
Research Blood (every 16 weeks)
	
Physical examination , CBC, Acute, Hepatic, Mineral Panels, LDH, CK, Uric Acid, Total Protein, TBNK, PSA, testosterone, PAP, dihydrotestosterone (DHT), sex hormone-binding globulin (SHBG), dehydroepiandrosterone (DHEA), luteinizing hormone (LH), follicle-stimulating hormone (FSH), androstenedione prolactin, estradiol
 
Research Blood (every 16 weeks)

*Apheresis is not mandatory and will be scheduled based on availability

-Patients may come off study before week 52 as clinically indicated.

-All patient visits can be delayed by 1 week for logistical issues.

** Patients will be followed until PSA reaches baseline. Patients who continue to be followed for rising PSA but have not required ADT may be seen beyond the study period. The study period ends 52 weeks after enrollment unless patients receive a second course of enzalutamide, then study period ends 9 months after the end of the second course.

¹ As indicated in section 7.3, all subjects will be offered the opportunity to complete an NIH advanced directives form. This should be done preferably at baseline but can be done at any time during the study as long as the capacity to do so is retained. The completion of the form is strongly recommended, but is not required.

Version Date: 12/5/17

Abbreviated Title: Enzalutamide in non-met CSPC

